8. INTERVENTION DISCONTINUATION

The investigators will only discontinue a participant's intervention if the risk-benefit ratio for that participant changes substantially such that they would no longer meet the project's eligibility criteria. Examples include development of signs consistent with neurologic deficits or presentation of "red flag" symptoms. These circumstances will be identified by research personnel during study visits for treatment or assessments. If a participant is discontinued, we will continue to collect the self-report outcomes only.

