4.2 Exclusion Criteria

Any subject meeting any of the following exclusion criteria at baseline will be excluded from participation.

- I. No prior surgery to the lumbosacral spine
- II. Not currently pregnant
- III. Not currently receiving mind-body or exercise treatment for LBP from a healthcare provider (e.g., chiropractic, physical therapy, massage therapy, etc.)
- IV. No neurogenic signs including any of the following: positive ipsi- or contra-lateral straight leg raise test (symptoms reproduced $<45^\circ$); reflex, sensory, or strength deficit in a pattern consistent with lumbar nerve root compression
- V. No “red flags” of a potentially serious condition including cauda equina syndrome, major or rapidly progressing neurological deficit, fracture, cancer, infection or systemic disease

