5.2.2 Prohibited Interventions

Prohibited interventions during the study period include any mind-body or other interventional procedures including spinal manipulation, massage, exercise therapy, acupuncture, spinal injections, surgical procedures, etc. If any prohibited events occur these will be recorded as off-protocol events. Subjects will continue to participate in study-related treatments and assessments unless the off-protocol intervention changes the risk-benefit profile for the subject.

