5.3 Adherence Assessment

Treatment adherence will be assessed based on attendance at scheduled treatment sessions and compliance with treatment protocols during treatment sessions. Once enrolled, a participant will have forms in REDCap for each scheduled treatment session according to the participant's randomized group assignment. Treatment session forms will permit an evaluation of the number of scheduled sessions attended by each participant. For sessions that are attended, the treating clinician will information on the interventions provided and any reasons for non-adherence to protocols. The site study coordinator will monitor the forms at least monthly and discuss instances of non-adherence with the clinician. All off-protocol events will be recorded, such as the use of use of modalities (heat, cold, ultrasound, etc.), or application of manual therapy or exercise procedures not outlined in the protocol. For purposes of the data analysis per-protocol analyses we will define "adherence" as occurring when at least 80% of scheduled treatment sessions are attended. Attendance at <80% of scheduled sessions will be considered a protocol deviation.

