6.2.1.2 Screening

Once informed consent is obtained the following screening procedures will be completed within 72 hours to insure eligibility:

- Confirm age on the date of consent is between 18 – 60 years old.
- Confirm that the participant is not aware that she is pregnant.
- Confirm that the participant is not currently receiving other interventions for their LBP.
- Confirm that the participant is experiencing LBP defined as pain between the 12th ribs and buttock with or without symptoms that extend into the buttock(s) or leg(s). without “red flags” suggesting a possible non-musculoskeletal cause (recent trauma, unexplained weight loss, night pain, systemic illness)
- Participant completes the Oswestry disability index to insure the score is $\geq 20\%$
- Research assistant conducts the physical examination to insure no signs of neurologic deficit are present (positive ipsi- or contra-lateral straight leg raise test (symptoms reproduced $<45^\circ$); reflex, sensory, or strength deficit in a pattern consistent with lumbar nerve root compression)

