6.2.5 Completion/Final Evaluation

The final evaluation occurs 3 months after Baseline (*from Day 83 – Day 97*). The following assessments are performed at the final evaluation. If a participant wishes to terminate the study early, this is also the list of assessments we will attempt to complete at termination. Early termination will only be done at a participant's request or if a participant's risk-to-benefit ratio is substantially altered due to a change in status.

- Physical examination
- Self-report questionnaires
- Spine stiffness measures
- Multifidus activation measures

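### Section 8 ties a treatment stop to loss of eligibility and then keeps self-report outcomes only, so a related severe event outside the exclusions has no formal route to stop treatment and stay in full follow-up

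*Combined protocol and SAP*

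**What the plan says.** Three parts of the combined protocol and SAP matter here.

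- **Section 8 (Intervention Discontinuation)** limits an investigator-led stop to one situation: "if the risk-benefit ratio for that participant changes substantially such that they would no longer meet" the eligibility criteria. Its two examples are neurologic deficit and red-flag symptoms. After a stop, "we will continue to collect the self-report outcomes only".
- **Section 6.2.5 (Completion/Final Evaluation)** allows early termination at the participant's request, or if the risk-to-benefit "ratio is substantially altered due to a change in status". It sets no eligibility condition. For a participant who wants to leave early, it gives the final-visit measures and adds that "this is also the list of assessments we will attempt to complete at termination".
- **Section 9.3 (Definition of Populations)** commits to intention-to-treat analysis whatever the compliance. Section 9.6 makes stiffness and multifidus activation co-primary for Aim 1, and Oswestry and pain co-primary for Aim 2. It puts primary emphasis on 4 weeks, and Secondary Aim 2 prefers 3-month scores when protocols are ranked.

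**The concern.** The stricter test is attached to the milder step. Stopping treatment requires a risk-benefit change and loss of eligibility; ending study participation requires only the risk-benefit change. An investigator facing a related severe event that matches no exclusion criterion therefore has a written basis for study exit, but none for stopping treatment with follow-up continuing.

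What is at stake is outcome data. Stops caused by treatment-related events depend on the assigned components. One of the eight combinations gives no further treatment, so it cannot produce such events in Phase II. Measurements lost this way are linked to assignment, and the mixed model then relies on the missing-at-random assumption in Section 9.2 for participants whose scheduled visits could have been kept. Separately, a stop that does qualify under Section 8 still drops both mechanistic co-primaries, which the Aim 1 intention-to-treat analysis needs.

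**Working it through.** The plan gives no figure on this point to reproduce. The check compares the rules, then counts measurements.

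**Step 1. Which events already meet the Section 8 condition?**
- Neurologic deficit and red flags: exclusions IV and V in 4.2, with a wider red-flag list in 6.2.1.2 ("recent trauma, unexplained weight loss, night pain, systemic illness").
- Outside care for back pain: exclusion III ("Not currently receiving mind-body or exercise treatment for LBP from a healthcare provider"), so starting such care would end eligibility.
- Off-protocol procedures such as injections or surgery have their own rule in 5.2.2: the participant continues "unless the off-protocol intervention changes the risk-benefit profile for the subject". That exception covers treatments and assessments together, so it does not secure follow-up.

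**Step 2. What is left?** Section 7 expects increased pain, soreness, spasm and psychological distress. None is an exclusion criterion. Section 7.4 grades severity but attaches no treatment action to a grade. Take a severe, related pain flare or spasm with no neurologic sign, red flag or outside care:
- Section 8 stop: not available, because eligibility is not lost.
- Section 6.2.5 early termination: available on risk-benefit.
- Section 7.5: follows the event to resolution or stabilization, not the trial outcomes.
- Sections 9.4 and 11.4: concern enrollment or the whole study, not one participant's treatment.

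**Step 3. Can treatment be withheld informally?** Section 5.3 counts attendance and has the clinician record reasons for departing from protocol. A session attended with one component withheld is not a missed session. Non-attendance is different: "Attendance at <80% of scheduled sessions will be considered a protocol deviation". Phase II has 6 sessions and the whole course has 8.
- One missed: 5/6 = 83.3%, or 7/8 = 87.5%; both above 80%.
- Two missed: 4/6 = 66.7%, or 6/8 = 75.0%; both below 80%.

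A deviation does not end follow-up. Withholding a component is therefore workable and documented, but it is not a formal stop rule.

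**Step 4. Scheduled co-primary measurements per affected participant**, for an event after randomization and before the 4-week assessment. The total is 4 outcomes × 2 visits (4 weeks, 3 months) = 8.
- Early termination before Day 29: 0 of 8 at scheduled visits, plus one set of 4 attempted at termination.
- Early termination with that set taken in the 4-week window (Days 29–42; Phase II visits run to Day 35): 4 × 1 = 4 of 8.
- Section 8 stop as written: 2 self-report outcomes × 2 visits = 4 of 8, with none of the 4 Aim 1 measurements.
- With the fix: up to 8 of 8.

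**Step 5. Scale against planned losses.** Section 9.2 gives 4-week retention as 95% in one sentence and 92% in another. With 280 enrolled, losses are 280 × 0.05 = 14 or 280 × 0.08 = 22.4, about 22. A few event-driven exits fit inside that allowance, so power is not the issue.

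**The case against.** The strongest reply is that Sections 6.2.5 and 8 are one rule. Both turn on a substantial risk-benefit change. The follow-up sentence in Section 8 speaks of a discontinued participant, not a discontinued intervention, and the one-time assessment list in 6.2.5 is introduced for a participant who wants to leave. On that reading an investigator-led discontinuation keeps self-report follow-up and 4 of 8 measurements, whenever it occurs. This is a fair reading, and it rules out the claim that study exit without follow-up is the only possible outcome. It does not reconcile the two triggers, and it does not recover stiffness and multifidus activation.

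Other points also stand. The remaining case is narrow: many severe events would bring neurologic signs, red flags or outside care. The protocol reports no adverse events in its earlier use of the manipulation techniques, the exercises and the stiffness measurement. Section 9.2 does more than assume missing at random: it compares participants with and without 4-week data, and applies multiple imputation with auxiliary variables if they differ substantially or losses exceed expectation. A few exits might trigger neither condition, so the protection is partial. Self-report-only follow-up is sensible for the present examples, where a prone indentation test may be unwise. A narrow trigger that favors continued treatment is also a legitimate choice, since treating clinicians are unblinded.

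A reader might infer that the protocol obliges a harmed participant to go on with treatment. It does not: 6.2.5 applies, the participant may decline or leave, and a component may be withheld under 5.3.

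**Conclusion.** The point holds as an inconsistency between two written rules, with a modest consequence for follow-up. Read literally, a related severe event outside the exclusion criteria has no formal investigator-led route to stop treatment with outcome follow-up continuing. Any Section 8 stop also ends collection of the Aim 1 co-primaries.

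Per affected participant the size is 0 to 4 of 8 scheduled co-primary measurements after early termination before the 4-week assessment, and 4 of 8 after a Section 8 stop, against up to 8 of 8. This assumes an event after randomization and, for the value of 0, that 6.2.5 is read as providing nothing beyond the termination assessment.

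It might also be inferred that the primary results will be materially biased or underpowered. The documents do not support that: they give no rate of such events, so neither a number affected nor a size of bias can be stated. Both are expected to be small. This is an inexpensive improvement to consider, not a flaw in the analysis.

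**What to change.** - **Section 8, trigger:** use the 6.2.5 risk-to-benefit trigger and drop the loss-of-eligibility condition. Keep neurologic deficits and red flags as examples, and add related adverse events that are graded severe or classed as serious.
- **Sections 8 and 6.2.5:** state that stopping the intervention is not early termination from the study.
- **Section 8, follow-up:** replace the self-report-only rule with all outcomes at the scheduled 4-week and 3-month visits, taking stiffness and multifidus measures where the investigator judges them safe.

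The cost is an IRB amendment to wording in two sections. The added measurements use visits already scheduled. A wider trigger may bring a few more treatment stops, decided with knowledge of the assigned treatment, which would slightly dilute the component contrasts. Those participants stay in the intention-to-treat analysis.

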9. STATISTICAL CONSIDERATIONS

9.1 General Design Issues

This study uses a factorial design examining 3 intervention components (additional SMT, mobilizing and multifidus activating exercise) provided in 8 different combinations following provision of 2 SMT treatment sessions. All participants will receive 2 SMT sessions. At the third session participants will be categorized as responders or non-responders based on a threshold of 50% improvement on the OSW. Randomization to subsequent treatment is stratified by responder status. We will randomly assign participants to receive 6 additional sessions (or no additional treatment) over 3 weeks with varied combinations of additional SMT and exercise co-interventions. It is important to distinguish the factorial design from an 8-arm trial. The factorial approach evaluates the main effects of the 3 additional intervention components (additional SMT, mobilizing and multifidus activating exercise) and interactions among components. It does not compare 8 distinct treatment arms and thus is more efficient with a smaller sample size relative to an 8-arm randomized trial.

Our primary hypothesis is that one or more combination of treatment components will optimize improvement in SMT mechanistic effects (reduction in spinal stiffness and improvement in multifidus activation) as well as improvement in patient-centered outcomes (LBP-related disability and pain intensity). Our secondary hypothesis is that responder status after 2 sessions will moderate the mechanistic and patient-centered outcomes. Our work and the work of others has demonstrated that these mechanistic and patient-reported outcomes are valid and can be collected reliably.

9.2 Sample Size and Randomization

Based on our past trials, we project 95% retention at 4-weeks. We estimated standard deviations of each outcome based on patients in a similar project with analogous eligibility criteria, and conservatively estimated pre-post correlations to be 4%-7% smaller than the values in this study. Assuming a sample size of 316, of which 280 meet all eligibility criteria and 92% of enrolled participants are retained to 4 weeks, the table below displays minimum detectable effect sizes for a) main effects of each protocol component, b) pairwise interactions between components, c) comparison of mean outcome between two levels of one component at a fixed level of another component, d) main effects of the 3 components in subgroup analyses involving half the participants, and e) pairwise interactions between 2 components in subgroup analyses with half the participants. This sample size provides at least 80% power to detect the MCID or hypothesized effect sizes for the main effects of each component for all outcomes, and for analyses of main effects in subgroups and conditional comparisons for each outcome except global stiffness. Power is more limited for secondary aims, such as pairwise interactions within subgroups.

	Assumptions for Outcome Measures in Project			
	Global Stiffness (N)	Multifidus Activation (mm)	Oswestry	Numeric Pain Rating
Assumption				
Mean (SD)	5.55 (1.60)	2.60 (0.124)	24.3 (14.9)	5.06 (2.12)
Pre-post score correlation	0.80	0.70	0.70	0.45
MCID or hypothesized effect size from past work	0.40	0.074	6.0	2.0
Type of effect	Detectable Effect Size			
Main effect	0.37	0.034	4.12	0.76
Pairwise interaction	0.74	0.064	8.24	1.53
Conditional comparison	0.53	0.045	5.83	1.08
Main effect in 50% of subjects	0.53	0.045	5.83	1.08
Interaction in 50% of subjects	1.05	0.091	11.65	2.16

Table. Assumptions and detectable effect sizes informing sample size for the project.

Because the analyses of the longitudinal models will be based on restricted maximum likelihood estimation, statistical inferences will remain valid so long as missing data follow a missing at random structure, and based on our past work we expect little missing data at the 4 week assessment. Thus we do not believe missing data will lead to substantial bias in our primary evaluation of protocol components. However, we will compare subject characteristics between subgroups with missing and nonmissing data at 4 weeks and if substantial deviations are detected, or the rate of missing data is greater than expected, multiple imputation will be applied using comprehensive imputation models which include auxiliary variables to account for additional predictors of missingness and/or the values of the outcome variables.

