3. STUDY DESIGN

We will use a factorial design examining 3 intervention components (additional SMT, mobilizing and multifidus activating exercise) provided in 8 different combinations following provision of 2 SMT treatment sessions as in our prior work. We will recruit 316 subjects with non-specific LBP with the goal of enrolling 280 subjects after all eligibility screening are complete. All subjects will receive the 2-session SMT protocol used in our prior studies. At the third session subjects will be categorized as SMT responders or non-responders based on our previously-validated threshold of 50% improvement on the Oswestry (ODQ). Randomization to subsequent treatment will be stratified based on responder status. This will allow us to examine the moderating effects of early clinical response. In our prior studies 35%-45% of individuals with LBP are responders to SMT after 2 sessions. What is unknown is the persistence of the improvement observed in early responders and whether or not persistence can be augmented through additional SMT and/or co-interventions working on the same causal pathways as SMT. Likewise, it is unknown from our prior work if early non-responders can be converted to responders with additional SMT and/or co-interventions. Therefore, we will randomly assign subjects to receive 6 additional sessions (or no additional treatment) provided over 3 weeks with varied combinations of additional SMT and exercise co-interventions. We chose 6 additional sessions based on work related to SMT dose-response reporting only modest difference in clinical outcomes in subjects receiving 9-12 sessions relative to 3-6 SMT sessions without co-interventions. Outcomes including assessments of

Outline of research design (LM = lumbar multifidus)

mechanisms and patient-centered outcomes will be examined at baseline and after 1 week (end of phase I), 4 weeks (primary outcome - end of phase II), and after 3 months (long-term outcome).

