6.2.2.3 Randomization

Following baseline assessment all participants will receive 2 SMT treatment sessions in the next week. Randomization to additional treatment will be done at the 1-week assessment. A randomization schedule will be developed prior to enrollment by co-investigator [name], Director of the Study Design and Biostatistics Center (SDBC) in the CCTS at the University of Utah. Blocked randomization with block sizes of 4 or 6 will be used. Randomization will be stratified based on site (Utah or Alberta) and responder status after 2 SMT sessions (based on re-assessment of the OSW) to balance these variables. At the 1-week assessment the study coordinator or research assistant will look up the participant in the study database and open the Responder & Randomization Status

form in REDCap. This form will display the Oswestry score from the baseline assessment and the calculation of score change. The percent change between baseline and 1-week scores determines responder status (>50% improvement = “responder”; <50% improvement= “non-responder”). Once the responder status is entered the study staff will select the randomize button on the screen to trigger study assignment based on the allocation table provided by the biostatistician, provided all of eligibility criteria are met and the participant has been assigned to one of the two study sites. If any of these criteria are not valid a warning message will be displayed indicating the criteria issue(s) and the randomization will not be completed.

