9.6 Data Analyses

Primary Aim 1: Spine stiffness and multifidus activation will be co-primary outcomes for evaluating effects of SMT protocol components on SMT mechanisms. The effect of intervention components (A additional SMT; B multifidus activation; C mobilizing exercises) on each outcome will be evaluated using linear mixed models to relate mean levels of each outcome at 1-, 4-weeks and 3-months to indicator variables to represent the main effects of each interventions (A, B, C) as well as each pairwise interaction between the interventions (AxB, AxC, BxC) and the 3-way interaction (AxBxC). 1-week assessment, which occurs just before randomization, will serve as the baseline for these analyses and the model will be assumed equal between the randomized groups. This model, sometimes referred to as a constrained longitudinal model, leads to adjustment for baseline levels as in analysis of covariance (ANCOVA), which has been shown to remove conditional bias in treatment group comparisons due to chance imbalances and improve statistical power over unadjusted comparisons. An unstructured covariance matrix will be used to account for correlation of serially measured outcome scores in the same subject. By using an unstructured covariance matrix, the model will constitute a special case of a general linear mixed model which avoids imposing specific assumptions concerning distribution of random effects. This modelling approach is recommended in randomized trials when the number of follow-up outcome assessments is small. Restricted maximum likelihood estimation will be used for estimation of parameters and their associated standard errors.

Linear mixed effects analysis will provide estimates and CIs for the following quantities for each outcome at both 4-week and 3-month assessments: a) Main effects evaluating effects of each of the 3 interventions while averaging over the levels of the other 2 interventions. b) Three pairwise interactions evaluating if the effect of an intervention differs between levels of another interventions, while averaging over levels of the 3rd intervention. Pairwise interactions will inform whether the effects of each intervention pair are additive, synergistic or antagonistic. c) 3-way interaction evaluating if each pairwise interaction differs depending on the 3rd intervention.

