Adjusted means with CIs will be provided for each treatment combination. Interaction plots will be used to depict significant interactions and linear contrasts constructed to evaluate the effect of each intervention conditional on the presence or absence of the other intervention. To account for 2 primary outcomes, each of the hypothesis tests noted above will be performed with 2-sided $\alpha=0.025$ and confidence intervals will be constructed using a confidence coefficient of 0.975. The indicated comparisons at 4-weeks will be given primary emphasis in evaluating the effects of each intervention. Comparisons at 3-months will evaluate persistence of effects following intervention.

Primary Aim #2: The OSW and NPRS will be co-primary outcomes for evaluating the effects of the 3 SMT protocol components on patient centered outcomes. The same analytic approach described above will be used. To account for 2 outcomes, we will again apply a 2-sided $\alpha=0.05$ and 97.5% CIs for statistical inference.

Secondary Aim #1: It is unknown how early SMT response may affect response to additional intervention. We will examine this question by evaluating responder status after 1 week as a possible effect moderator by adding a main effect for responder status and interaction terms between responder status and the indicator variables for treatments (and treatment combinations) which are retrained in the final simplified models for the different outcomes developed using the BIC criteria for each of the co-primary outcomes for the primary aims 1 and 2. Statistically significant interactions between responder status and main effect and/or interaction terms between treatment intervention components will be interpreted as suggesting effect moderation. Recognizing that tests for interactions have limited statistical power, we will also fit the simplified models developed in Aims 1 and 2 separately under the presence and absence of each factor (dichotomizing using a median split for continuous factors), and graphically display the estimated treatment effects at both levels of responder status. Recognizing the potential for lower statistical power, the results of Secondary Aim #1 will be interpreted as exploratory.

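### Primary Aim 2 is set at alpha 0.05 although its 97.5% intervals and the Oswestry power figures imply 0.025; separately, the Oswestry subgroup power claim holds only for subgroups of about half the participants or more

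*Combined protocol and SAP*

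**What the plan says.** **Alpha.** Section 9.6 gives each primary aim two co-primary outcomes. For Primary Aim 1 (stiffness and multifidus activation) every test is two-sided at 0.025, with a confidence coefficient of 0.975, because there are two outcomes. For Primary Aim 2 (Oswestry and pain) the plan repeats the analytic approach and the reason for adjusting. It then states a two-sided alpha of 0.05 with 97.5% intervals. Section 9.2 does not say which alpha its table of detectable effects uses.

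**Subgroup power.** Section 9.2 credits the sample size with at least 80% power for the MCID or hypothesized effect, for main effects and also "for analyses of main effects in subgroups and conditional comparisons for each outcome except global stiffness". The supporting row is defined as "main effects of the 3 components in subgroup analyses involving half the participants". For Oswestry it prints 5.83 against an MCID of 6.0. The only moderator the plan names is responder status, and Section 3 reports: "In our prior studies 35%-45% of individuals with LBP are responders to SMT after 2 sessions". Section 9.6 adds separate fits: "Recognizing that tests for interactions have limited statistical power, we will also fit the simplified models developed in Aims 1 and 2 separately". It labels Secondary Aim 1 exploratory and acknowledges lower power.

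**The concern.** The Aim 2 rule contradicts itself. A test at 0.05 and a 97.5% interval give different answers whenever the p-value lies between 0.025 and 0.05: the result is significant, yet the interval includes zero. An alpha of 0.05 for each of two outcomes also makes no adjustment, although adjustment is the stated purpose. This affects a primary aim, and two analysts could report the same Oswestry or pain result differently while both followed the plan.

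The subgroup sentence matters less. It does not repeat the half-sample basis of its row, and the Oswestry margin is thin. A reader interpreting a null Oswestry result in responders could take the 80% as applying to them, when the prior-study share of responders is below one half.

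**Working it through.** **Inputs.** From 9.2: Oswestry SD 14.9; pre-post correlation r = 0.70; 280 eligible with 92% retained, so N = 280 × 0.92 = 257.6; power 80%; MCID 6.0. Participants are randomized equally over eight combinations, so each component's main effect is a 1:1 comparison.

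**Formulas.**
- Residual SD = 14.9 × √(1 − 0.70²) = 10.64
- SE(main effect) = 10.64 × √(4/n)
- Detectable effect = (z(1−α/2) + z(0.80)) × SE; the multiplier is 2.241 + 0.842 = 3.083 at α = 0.025 and 1.960 + 0.842 = 2.802 at α = 0.05
- Power for 6 points = Φ(6/SE − 2.241) at α = 0.025

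**1. Reproducing the Oswestry column.** In the full sample SE = 10.64 × √(4/257.6) = 1.326.

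| Oswestry row | Printed | α = 0.025 | α = 0.05 |
|---|---|---|---|
| Main effect | 4.12 | 4.09 | 3.71 |
| Main effect in 50% | 5.83 | 5.78 | 5.25 |

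At 0.025 both rows agree within 1%, and a noncentral-t version gives 4.11 and 5.84. To obtain 4.12 at 0.05, N would have to be (2.802 × 2 × 10.64 / 4.12)² ≈ 209, about 75% of 280, which is not a figure in the plan. The pain main effect is not matched exactly by either alpha (printed 0.76; 0.73 at 0.025, 0.66 at 0.05), so the inference rests on Oswestry.

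**2. Consequence of 0.05 per outcome.** The chance of a false positive on at least one of the two outcomes, for one component effect, is at most 2 × 0.05 = 0.10 (1 − 0.95² = 0.0975 if the outcomes were independent). At 0.025 each, the bound is 0.05.

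**3. Subgroup claim at half the participants.** With n = 128.8, SE = 1.875 and power for 6 points is Φ(3.200 − 2.241) = 83%. The sentence is correct on its stated basis.

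**4. Smallest share that keeps 80% for Oswestry.** From the printed row alone: 0.5 × (5.83/6.0)² = 47.2%. From the formula: (4.088/6)² = 46.4%.

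**5. Illustration at the prior-study responder share** (SD 14.9, r 0.70, 92% retention and α = 0.025, all assumed to hold within responders):

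| Share | n | SE | Detectable effect | Power for 6 points | Power at 95% retention |
|---|---|---|---|---|---|
| 35% | 90 | 2.241 | 6.91 | 66.8% | 68.4% |
| 40% | 103 | 2.097 | 6.46 | 73.3% | 74.8% |
| 45% | 116 | 1.977 | 6.09 | 78.6% | 80.0% |

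The last column uses N = 280 × 0.95 = 266, since 9.2 also says: "Based on our past trials, we project 95% retention at 4-weeks".

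Section 9.2 also describes r as cautious: "conservatively estimated pre-post correlations to be 4%-7% smaller than the values in this study". Undoing that discount as a relative one gives r = 0.70/0.96 = 0.729 to 0.70/0.93 = 0.753. At 92% retention, power is then 71.0-74.6%, 77.2-80.6% and 82.3-85.3% at the three shares.

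The complementary non-responder group (55-65%) has 86.7-92.0% power for Oswestry on the planning inputs. In responders, multifidus activation has 96-99% and pain above 99%.

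**The case against.** **On alpha.** One could argue that 0.05 per outcome is legitimate if both co-primary outcomes had to succeed. The plan sets no such condition. It gives the number of outcomes as the reason for adjusting, and 97.5% intervals would still not match a 0.05 test. Nor does the slip show that the trial was sized at the wrong level, as a reader might infer: the Oswestry figures fit 0.025.

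**On subgroups.** A reader might infer that the 80% claim is an arithmetic error, or that the trial is underpowered. The documents support neither, and most of the case against those readings stands.
- The half-sample basis is stated in the text and in the row label, and the figure is right there. Section 9.6 mentions median splits for continuous factors, which produce half-size subgroups and explain the row, although responder status is binary.
- The 35-45% share describes prior studies. It is not a planning input in 9.2.
- Moderation is judged from interaction terms. The separate fits are displayed graphically, with no stratum-level test or decision rule, in an exploratory aim.
- Whole-sample SD and r may not hold within strata. Responders are selected on Oswestry itself ("The percent change between baseline and 1-week scores determines responder status") and the analysis starts from the 1-week score ("1-week assessment, which occurs just before randomization, will serve as the baseline for these analyses"). A residual SD lower by 1.5%, 7.2% or 13.2% would restore 80% at 45%, 40% or 35%; it could also be higher. The documents give no stratum values.

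What remains is that the sentence omits the limit its own figures impose, and for Oswestry that limit lies just below one half.

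A reader might also infer from 8.24 against 6.0 that the plan overclaims power for pairwise interactions. It does not: 9.2 claims no 80% power for them and prints the figure.

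**Conclusion.** The Aim 2 alpha is wrong as written. It conflicts with its own intervals, with the stated adjustment for two outcomes, with the parallel rule for Aim 1 and with the Oswestry detectable effects. The error is up to 0.10 instead of 0.05 per component effect across the two outcomes, with contradictory conclusions for p-values between 0.025 and 0.05. That 9.2 used 0.025 is inferred from reproducing the Oswestry column, because 9.2 names no alpha.

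The subgroup point is secondary and conditional. The claim is correct at half the participants and, for Oswestry on the planning inputs, down to about 46-47%. The responder figures are illustrative and depend on whole-sample inputs holding within the stratum. The shortfall is negligible at a 45% share (none at 95% retention) and material at 35%. It also depends on the alpha: at 0.05, planning-input power would be 76%, 82% and 86% at 35%, 40% and 45%. Non-responders, multifidus activation and pain are unaffected.

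**What to change.** 1. In 9.6, Primary Aim 2, change the two-sided alpha from 0.05 to 0.025 and keep the 97.5% intervals. State in 9.2 that the detectable effects use 0.025, once the sponsor has confirmed this against the original calculation.
2. In 9.2, limit the Oswestry part of the subgroup claim to subgroups of about half the participants or more.
3. Optionally, add an illustrative Oswestry detectable effect for responders of about 6.1-6.9 points at a 45-35% share, naming the assumptions (SD 14.9, r 0.70, 92% retention, alpha 0.025, all taken to hold within responders).

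The cost is one alpha value in 9.6 and a few words in 9.2. Sample size, models and the exploratory status of Secondary Aim 1 do not change.
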